7. GENERAL CONSIDERATIONS

7.1 Reference Start Date

Study Day will be calculated from the reference start date, and will be used to assign corresponding study visits of assessments or events.

Reference start date is defined as the day of the first dose of study medication, (Day 1 is the day of the first dose of study medication). In case the first dose date is missing, the randomization date will be used instead.

- If the date of the event is on or after the reference start date then:
Study Day = (date of event – reference start date) + 1.
- If the date of the event is prior to the reference start date then:
Study Day = (date of event – reference start date).

If the situation where the date of assessment or event is partial or missing, the date will appear partial or missing in the listings, and unless otherwise specified in the relevant section, Study Day and any corresponding visit will be assigned based on the imputations specified in Appendix 1; Partial Date Conventions.

7.2 Baseline

Except for the lipid parameters for which Visit 1 measurement will be used as the baseline, baseline is defined as the last non-missing measurement taken prior to reference start date. In the case where the last non-missing measurement and the reference start date coincide, that measurement will be considered pre-baseline, but Adverse Events (AEs), medications, and medical procedures commencing on the reference start date are considered post-baseline.

7.3 Windowing Conventions

Protocol-defined assessments will be assigned to study weeks based on collection date and applying the rules summarized in the following table. If there is more than one scheduled visit in a visit window, the visit closest to the target date will be used. If there is a tie between the numbers of days from the target date, the visit after the target date will be used. Unscheduled visits that fall within the protocol-defined visit windows will be summarized in the by-visit analyses if there is no

Document: Document path and title

Template No.: CCI

Reference: CCI

Effective Date: 15Oct2021

scheduled visit available. If there is more than one unscheduled visit within the protocol-defined visit window and no scheduled visit available, the unscheduled visit closest to the scheduled visit date will be used. If there is a tie between the numbers of days from the target date, the visit after the target date will be used.

Visit	Visit 1 (screening)	Visit 2	Visit 3	Visit 4
Assigned Study Week	-1	0	6	12
Target Study Day	-7	1	43	85
Analysis Visit Windows	[-7, 1*]	[1,1]	[**14,64]	[65,105]

* Visit 1 and Visit 2 may be conducted on the same date.

** Target Day 2 to Target Day 13 will be assigned as unscheduled visit 2.x.

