1.3 Schedule of Activities

Table 1-1 presents the schedule of activities (SoA).

Table 1-1 Schedule of Activities

Procedure	Screening ^{a)}	Intervention Period			E/D
	-D7~D1	W0	W6	W12/EOS	
	V1	V2	V3	V4	
Visit window			± 7 days	± 7 days	
Informed consent ^{b)}	X				
Inclusion and exclusion criteria	X				
Demographics	X				
Physical examination (height, weight) ^{c)}	X	X	X	X	X
Medical history related to dyslipidemia	X				
General medical history	X	X			
Prior medication ^{d)}	X				
Serum or urine pregnancy test (WOCBP only)	X	X	X	X	X
12-lead ECG	X	X	X	X	X
Vital signs ^{e)}	X	X	X	X	X
TLC ^{f)}	X	X	X	X	X
Randomization		X			
IMP distribution and return ^{g)}		X	X	X	
Concomitant therapy		X	X	X	X
Lipid parameter laboratory tests ^{h)}	X	X	X	X	X
General laboratory tests	X	X	X	X	X

Procedure	Screening ^{a)}	Intervention Period			E/D
	-D7~D1	W0	W6	W12/EOS	
	V1	V2	V3	V4	
Visit window			± 7 days	± 7 days	
AE/SAE review		X	X	X	X

Abbreviations: AE = adverse event; D = day; ECG = electrocardiogram; EOS = end of study; E/D = early discontinuation; IMP = investigational medical product; SAE = serious adverse event; TLC = therapeutic lifestyle change; V = visit; W = week; WOCBP = women of childbearing potential.

- a) Screening test (Visit 1) will be performed in the local laboratory and results may be substituted if available within 2 weeks prior to the screening visit. The Visit 1 and Visit 2 may be conducted on the same day.
- b) All procedures related to clinical trials must be carried out after obtaining written consent, and screening numbers are assigned in the order of written consent.
- c) Height is measured at screening only and body weight will be measured at each visit.
- d) Prior medication up to 1 month prior to enrollment will be collected.
- e) Heart rate and blood pressure will be assessed. Vital signs will be measured in a relax position after 5 minutes rest.
- f) Participants will receive education on TLC methods and perform during the clinical trial period.
- g) IMPs are distributed at Visit 2 and Visit 3, and the remaining IMPs are returned at Visit 3 and Visit 4, respectively.
- h) All tests will be performed in the local laboratory.

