4. STUDY DESIGN

4.1 General Description

This is a phase 4, multicenter, randomized, open-label, active-controlled study. The study has been designed to evaluate the effectiveness and safety of early add-on of ezetimibe with atorvastatin in very high-risk patients.

In Visit 1, screening is conducted for patients in the very high-risk group. LDL-C needs to be above 70 mg/dL in patients (a) who failed to achieve their target LDL-C goals with mild to moderate intensity statin; (b) who are statin-naïve or have not been on a stable statin regimen for at least 4 weeks prior to enrollment. However, by tracking the registration status of patients, (b) patients should be enrolled not to exceed 40% of each group. All laboratory tests are performed in the local laboratory and the Visit 1 results may be substituted if available within 2 weeks prior to the screening visit. The study participation is determined through the inclusion/exclusion criteria based on the test results conducted for Visit 1. In the case of the lipid parameter, Visit 1 results are used as the baseline. Individuals who do not meet the criteria for participation in this study (screen failure) may be rescreened once.

In Visit 2, randomization is performed on patients who meet the inclusion criteria and do not meet any of the exclusion criteria and will be distributed 1:1 between test group (arm Eze/Ato) and control group (arm Ato). The results of laboratory tests at the Visit 2 are used as baseline except lipid parameters. Visit 1 and Visit 2 may be conducted on the same date.

In Visit 2 and Visit 3, the appropriate investigational medical product (IMP) is given to each group. In principle, IMPs are administered orally once a day from the day of distribution.

Document: Document path and title

Template No.: CCI

Reference: CCI

Effective Date: 15Oct2021

[figure not shown]

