15. EFFECTIVENESS OUTCOMES

15.1 Primary Effectiveness

15.1.1 Primary Effectiveness Variable & Derivation

The primary objective of this study is to evaluate the effectiveness of early add-on of ezetimibe with atorvastatin in very high-risk patients.

The primary endpoint is percentage change in LDL-C from baseline (Visit 1) to week 6 (Visit 3).

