15.1.2 Primary Analysis of Primary Effectiveness Variable

The primary endpoint analysis will be performed on the FAS.

The statistical hypothesis of this study is as follows.

$$H_0: \mu_t - \mu_c = 0 \text{ vs. } H_1: \mu_t - \mu_c \neq 0$$

Document: Document path and title

Template No.: CCI

Reference: CCI

Effective Date: 15Oct2021

μ_t = Percentage change in LDL-C from baseline to 6 weeks in ezetimibe/atorvastatin 10/40 mg
 μ_c = Percentage change in LDL-C from baseline to 6 weeks in atorvastatin 40 mg

The primary endpoint will be analyzed by fitting an ANCOVA model with treatment group (Eze/Ato, Ato) and history of statin administration (Yes, No) as fixed effects and baseline LDL-C as a covariate. In addition to descriptive statistics for LDL-C at each visit and its percentage change from baseline by treatment group, least squares (LS) means for each treatment group with corresponding standard errors (SEs) and treatment differences of LS means with corresponding two-sided 95% confidence interval (CI) and p-value which will be derived from the fitted model will be presented. If the upper limit of the 95% two-sided CI for the corresponding treatment difference (Eze/Ato - Ato) is less than 0, Eze/Ato is considered superior to Ato.

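### Does the Visit 1 window of Day -7 to Day 1 in SAP 7.3 shut out older lipid results allowed as baseline, and can its nearest-to-target rule put a post-titration value into Week 6?

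*SAP*

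**What the plan says.** **Visits by date.** SAP 7.1 states that "Study Day will be calculated from the reference start date, and will be used to assign corresponding study visits of assessments or events". SAP 7.3 repeats the principle: "Protocol-defined assessments will be assigned to study weeks based on collection date and applying the rules summarized in the following table". Its table sets Visit 1 at Day -7 to 1, Visit 2 at Day 1, Week 6 at Day 14 to 64 (target Day 43) and Week 12 at Day 65 to 105.

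**Baseline lipids.** SAP 4.1 provides that "the Visit 1 results may be substituted if available within 2 weeks prior to the screening visit", and note a to the protocol's Schedule of Activities (section 1.3) says the same: "results may be substituted if available within 2 weeks prior to the screening visit". SAP 7.2 then carves lipids out of the general baseline rule: "Except for the lipid parameters for which Visit 1 measurement will be used as the baseline". SAP 15.1.1 also defines the primary endpoint by nominal visit, from Visit 1 to Visit 3.

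**Choosing the Week 6 value.** SAP 7.3 says: "If there is more than one scheduled visit in a visit window, the visit closest to the target date will be used". Ties go to the visit after the target. Unscheduled visits count only when no scheduled one is available. The hypothesis in SAP 15.1.2 concerns the starting doses; its first term is "Percentage change in LDL-C from baseline to 6 weeks in ezetimibe/atorvastatin 10/40 mg".

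**The concern.** Baseline LDL-C is both the denominator of the primary endpoint and a covariate in its ANCOVA, so its source should not depend on which SAP section a programmer reads first. A programmer who applied 7.3 alone would assign a substitute from before Day -8, or on it, to no visit. The patient might then lack the baseline LDL-C that the FAS requires, or the Day 1 lipid sample from Visit 2, which also falls within Day -7 to 1, might be used instead.

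The Week 6 rule raises a separate question. The dose may rise at Visit 3, or at an additional visit within a week if the result is late. Nothing in 7.3 requires the Week 6 sample to precede that increase. The early-discontinuation visit includes lipid tests but has no row in the 7.3 table. If it counted as scheduled, a sample on the higher dose could enter a comparison of the starting doses.

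**Working it through.** **1. Reach of the substitution allowance.** Inputs: screening on Day -7 to Day 1 (protocol 1.3), substitutes 1 to 14 days before screening, no Day 0 (SAP 7.1), and first dose on the day of Visit 2.

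| Screening day | Permitted substitute days | Outside Day -7 to 1 |
|---|---|---|
| -7 | -21 to -8 | 14 of 14 |
| -4 | -18 to -5 | 11 of 14 |
| -1 | -15 to -2 | 8 of 14 |
| 1 (Visits 1 and 2 together) | -14 to -1 | 7 of 14 |

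The mismatch is real. These are calendar days, however, not patients.

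**2. Which rule decides the baseline.** Set side by side:

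- SAP 4.1 lets an earlier result stand in for the Visit 1 result, then names Visit 1 results as the lipid baseline. A permitted substitute is therefore a Visit 1 result.
- SAP 7.2 is the specific rule for lipids and has no date limit. SAP 7.3 is a general convention.
- SAP 4.1 takes baseline laboratory values from Visit 2 except for lipids, which excludes the Day 1 lipid sample as a replacement.
- Eligibility is judged on the Visit 1 results, and inclusion criterion 4 needs an LDL-C of at least 70 mg/dL. An eligible randomized patient therefore has a Visit 1 LDL-C, substituted or not.
- The window Day -7 to 1 matches the protocol's screening column, to which the substitution note is attached. There, the dates of the visit and an older laboratory result coexist.

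**3. What the wrong reading would cost.** The documents give no frequency, so any loss is an assumption. With a difference of 10 and SD 19 (SAP 4.2), power = Φ(10 / (19 × √(2/m)) − 1.96) for m analysed per group. At m = 57 this gives 0.80, the plan's own figure. Assumed losses of 5%, 10%, 20% and 30% of the 57 give 0.78, 0.76, 0.71 and 0.65. These apply only if 4.1, 7.2 and 15.1.1 are all ignored.

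**4. Week 6 displacement.** Let Visit 3 be on Day d < 43 and a later sample on Day e. If both count as scheduled, the later one is chosen when d < e ≤ 86 − d, with equality being the tie. The number of such days is 86 − 2d. If the dose rises 7 days after Visit 3, only Days d + 8 to 86 − d follow the increase, which is 79 − 2d days when positive.

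| Visit 3 (d) | Displacing days | Of these, after an increase at d + 7 |
|---|---|---|
| 36 | 37–50 (14) | 44–50 (7) |
| 37 | 38–49 (12) | 45–49 (5) |
| 38 | 39–48 (10) | 46–48 (3) |
| 39 | 40–47 (8) | 47 (1) |
| 40 | 41–46 (6) | none |
| 41 | 42–45 (4) | none |
| 42 | 43–44 (2) | none |
| 43 or later | none | none |

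The totals are 56 day pairs and 16 day pairs. With a same-day increase, all 56 follow it. A Visit 3 earlier than the protocol's ±7 days widens the interval: for d = 22, it reaches 86 − 22 = 64.

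A Visit 4 inside its protocol window (85 ± 7, Day 78 to 92) never enters Day 14 to 64. No lipid test is listed for the additional drug-supply visit. That leaves chiefly the early-discontinuation visit, and only if it counts as scheduled.

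**The case for a change.** The strongest case for a change is that SAP 7.2 does not say which record is Visit 1, whereas 7.1 and 7.3 define visits by date and state no exception for substitutes. The only note on the Visit 1 window concerns Visits 1 and 2 falling on one day. The patients not on a stable statin regimen, in a stratum capped at 40% of each group, may have LDL-C that is still moving, so a substitute and a Day 1 sample up to three weeks apart could differ. The status of the early-discontinuation visit is also undefined, and a few sentences would settle both points.

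It stands that the SAP states no order of precedence and does not classify the early-discontinuation visit. It does not stand that the baseline is open: the substitution and the lipid baseline are set together in 4.1, and 7.2 and 15.1.1 agree with it. The early-discontinuation column in the protocol has no visit number, week or window, and the 7.3 table gives target days only to Visits 1 to 4. The natural reading is that it is unscheduled and cannot displace an available Visit 3, which 15.1.1 also names as the Week 6 visit. Nor is a rule needed to keep values taken after treatment stops: the FAS analyses patients as randomized, and no SAP rule removes those values.

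**Conclusion.** No change to the plan follows. The baseline point is a missing cross-reference: the window omits up to 14 of the 14 permitted substitute days, but the sections that govern lipid baseline already give the intended value. The Week 6 point needs a patient whose Visit 3 falls before Day 43, who misses the target and is up-titrated, then leaves with a lipid sample within at most 14 days (for a Visit 3 on Day 36 or later), and whose exit visit is coded as scheduled against the natural reading.

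The number of patients in either situation is not in the documents, and no effect on the estimate, error rate or power has been shown. The conclusion assumes that programmers read SAP 7.3 together with 4.1, 7.2 and 15.1.1, and treat the early-discontinuation visit as unscheduled. The ordinary derivation specification can record both.

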7.4 Common Calculations

Change from baseline will be calculated as:

- Value at Week X – Value at Baseline

Percentage change from baseline will be calculated as:

- $100 \times (\text{Value at Week X} - \text{Value at Baseline}) / \text{Value at Baseline}$

7.5 Software Version

All analyses will be performed using SAS VIYA or above.

8. STATISTICAL CONSIDERATIONS

8.1 General Methodologies

Medical history, prior/concomitant procedures and AEs will be coded using the Medical Dictionary for Regulatory Activities (MedDRA) version 25.1 or later and summarized by MedDRA system organ class (SOC) and preferred term (PT), displayed by descending frequencies. Each patient will be counted only once within each SOC or PT.

Document: Document path and title

Template No.: CCI

Reference: CCI

Effective Date: 15Oct2021

Prior/concomitant medications will be coded using the World Health Organization Drug Dictionary (WHO-DD) version C3 Sep 2022 or later and summarized by therapeutic subgroup and preferred name, displayed by descending frequencies. Each patient will be counted only once within each therapeutic subgroup or preferred name.

Descriptive statistics will include number of patients without missing values, mean, standard deviation (SD), median, 1st quartile, 3rd quartile, minimum, and maximum for continuous variables, and the number of patients without missing values and the number and percentage of patients for each category for categorical variables.

8.2 Statistical Tests and Confidence Intervals

For continuous efficacy variables (except triglycerides), the statistical comparisons between treatment groups are performed using an analysis of covariance (ANCOVA) with treatment group and history of statin administration as factors and the corresponding baseline as a covariate. For categorical efficacy variables, the statistical significance of the differences between treatment groups is tested using Chi-square test or Fisher's exact test. All the statistical tests use a two-sided test at the significance level of 0.05.

Due to the known distribution of triglycerides, normality assumption is usually difficult to satisfy. A nonparametric approach will be used for the analysis of percent change from baseline for triglycerides. The Hodges-Lehmann method will be used to estimate the median difference and its corresponding 95% CI for percent changes between the treatment groups.

Inferential conclusion will be drawn only for primary endpoint based on p-value at 0.05 significance level as described in section 15.1.2 of this analysis plan.

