9.5 Sample Size Determination

The statistical hypothesis of this study is as follows.

$$H_0: \mu_t - \mu_c = 0 \text{ vs. } H_1: \mu_t - \mu_c \neq 0$$

$$\mu_t = \text{Percentage change in LDL-C from baseline to 6 weeks in ezetimibe/atorvastatin 10/40 mg}$$

$$\mu_c = \text{Percentage change in LDL-C from baseline to 6 weeks in atorvastatin 40 mg}$$

Azar et al. reported that the between-treatment difference in percentage change in LDL-C at 8 weeks was -10% in favor of ezetimibe/atorvastatin 10/40 mg compared to atorvastatin 40 mg (-20% vs -10%; p-value=0.01) (Azar RR 2010). This is the only study that has assessed the efficacy of ezetimibe/atorvastatin 10/40 mg versus atorvastatin 40 mg among very high-risk patients with stable CAD or CAD equivalent (coronary stenosis >50%, previous myocardial infarction, percutaneous coronary intervention, coronary artery bypass graft surgery, diabetes

mellitus, stroke, peripheral vascular disease) who were taking the potency of the background statins ≤ 20 mg/day of atorvastatin prior to the randomization. Although the evaluation time point for the LDL-C lowering effect in Azar et al. study is at 8 weeks, it is noted that a reduction in LDL-C is usually achieved with all statins as well as ezetimibe as early as 2 weeks, with a maximum response occurring by 4 weeks and maintaining thereafter during continued therapy (ACH-Ezetimibe Product Monograph 2019; Shankar PR 2019). Given that, this study sets -10% as the expected difference in percentage change in LDL-C from baseline to 6 weeks between the treatment groups.

The pooled standard deviation of 19.0% was obtained from the p-value of 0.01 and a total of 50 patients per treatment group reported in the study of Azar et al.; The t-value that corresponds with a p-value of 0.01 and $50 + 50 - 2 = 98$ degrees of freedom is $t=2.627$, considering that the degrees of freedom are given $N_1 + N_2 - 2$, where N_1 and N_2 are the number of study patients per each treatment group. As the t-value is the ratio of the difference in means to the standard error of the difference in means, the standard error is therefore obtained by dividing 10 (treatment difference in percentage change in LDL-C) by 2.627, which gives 3.8066. In turn, the standard deviation obtained from standard error is 19% ($3.8066 / \text{SQRT}(1/50 + 1/50)$).

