Based on this, the number of patients in each treatment group calculated by the formula below is about 57 under the assumption of two-sided significance level $\alpha = 0.05$, power $1-\beta = 0.80$ with a randomization ratio $\lambda = 1$. Considering the dropout rate of 10%, 63 patients for each group and thus, a total of 126 patients will be randomized in this study.

$$n = \frac{(\gamma + 1)(Z_\alpha + Z_\beta)^2 \sigma^2}{\gamma(\mu_t - \mu_c)^2} = \frac{(1 + 1)(1.96 + 0.842)^2(19)^2}{(-10)^2} = 56.69$$

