For patients whose LDL-C value has reached the target (LDL-C < 55 mg/dL) according to the lipid indicator test at Visit 3, they will continue treatment with the same dose for 6 weeks. If the LDL-C level has not reached target, the dose of atorvastatin should be increased to ezetimibe/atorvastatin 10/80 mg or atorvastatin 80 mg according to the group assigned. In principle, a morning visit is recommended so that the laboratory test results can be checked, and the IMP can be prescribed and taken on the same day. However, if the test results are not confirmed on the same day and a patient has enough IMP to take until the next visit, IMP compliance is checked, and the same dose of IMP (ezetimibe/atorvastatin 10/40 mg or atorvastatin 40 mg) is continued. An additional visit is made within 1 week to return the remaining IMP and receive new IMP. If the test results are not confirmed on the same day and a patient does not have remaining IMP, the investigator prescribes the same dose of IMP (ezetimibe/atorvastatin 10/40 mg or atorvastatin 40 mg) that the patient was taking previously, and an additional visit is made within 1 week to receive new IMP. Visit 4 is the end of study visit, and tests for effectiveness and safety are conducted.

Document: Document path and title

Template No.: CCI

Reference: CCI

Effective Date: 15Oct2021

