15.2.2 Missing Data Methods for Secondary Effectiveness Variable(s)

No missing data imputation will be used for the analysis of the secondary effectiveness variables.

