15.2.3 Analysis of Secondary Effectiveness Variables

All secondary endpoint analyses will be performed on the FAS.

The number and percentage of patients achieving LDL-C goal of < 55 mg/dL and LDL-C goal of < 70 mg/dL at 6 weeks and 12 weeks will be presented by treatment group and tested using Chi-square test or Fisher's exact test as appropriate. The difference in the percentage will be presented with its corresponding 95% CI and p-value.

The continuous secondary endpoints (except triglycerides) will be analyzed by fitting ANCOVA models with treatment group (Eze/Ato, Ato) and history of statin administration (Yes, No) as fixed effects and baseline value of interest as a covariate. In addition to descriptive statistics for variables of interest at each visit and its percentage change at a period from baseline by treatment group, LS means for each treatment group with corresponding SEs and treatment differences of LS means with corresponding two-sided 95% CIs and p-value will be presented. The ANCOVA model will be fitted separately at 6 weeks and 12 weeks.

A nonparametric approach will be used for the analysis of triglycerides (percent change from baseline). The Hodges-Lehmann method will be used to estimate the median difference and its corresponding 95% CI for percent changes between the treatment groups.

Document: Document path and title

Template No.: CCI

Reference: CCI

Effective Date: 15Oct2021

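### The Week 12 LDL-C comparison discards the Week 6 value of patients lost after Visit 3, and no planned analysis covers that loss; the likely bias is small and its direction depends on how loss differs by arm.

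*SAP*

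**What the plan says.** SAP 8.2 gives the model for lipids other than triglycerides: "For continuous efficacy variables (except triglycerides), the statistical comparisons between treatment groups are performed using an analysis of covariance (ANCOVA", with treatment and statin history as factors and the lipid's own baseline as covariate. The Week 6 result is not a term in the Week 12 model. SAP 15.2.3 adds: "The ANCOVA model will be fitted separately at 6 weeks and 12 weeks". SAP 15.2.2 adds: "No missing data imputation will be used for the analysis of the secondary effectiveness variables". Together these make the Week 12 analysis complete-case.

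The planned sensitivity analyses do not reach Week 12 loss:
- LOCF (SAP 8.4 and 15.1.3) is restricted to missing Week 6 LDL-C.
- The only sensitivity analysis for secondary endpoints is the PPS (SAP 15.2.4). Its completion requirement (SAP 6.2) stops at Week 6.

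Protocol 9.3.1 had LOCF as the default for every efficacy parameter, which would have carried Week 6 values to Week 12. The SAP removes that rule and takes precedence over the protocol's statistical sections (SAP 2), yet SAP 4.5 reports no change from the protocol. The SAP's revision history for version 1.2 does mention the move away from LOCF, so the change is on record, but not where a reader would look for it.

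**The concern.** Week 6 LDL-C is not a passive measurement in this trial. It sets the Visit 3 dose: "If the LDL-C level has not reached target, the dose of atorvastatin should be increased" (SAP 4.1). The trial is open-label and tested in local laboratories, so sites know the result and patients can. A patient's decision, or an investigator's, to stop before Visit 4 could plausibly follow from it.

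If so, the patients with a Week 12 value are a selected group, and treatment, baseline and statin history do not describe the selection. More control patients should have poor Week 6 values if ezetimibe works. A common tendency for poor responders to leave would then remove more of the control arm's worst values and shrink the Week 12 difference. The Week 6 results of those patients are already in the database and would correct most of this, but the planned model cannot use them.

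At stake are the Week 12 LDL-C estimate, its interval and its p-value. The Week 6 primary analysis is not affected.

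**Working it through.** **Inputs from the documents (Protocol 9.5).** Difference: "this study sets -10% as the expected difference in percentage change in LDL-C from baseline to 6 weeks between the treatment groups". SD: "The pooled standard deviation of 19.0% was obtained from the p-value of 0.01". Two-sided alpha 0.05, power 0.80, 1:1 allocation, 10% dropout, 63 per arm. No Week 12 effect, power or dropout figure is given.

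**The plan's own figure.** n = 2 × (1.96 + 0.842)² × 19² / 10² = 56.69, about 57 per arm. 56.69 / 0.9 = 62.99, so 63 per arm. Both stated figures reproduce (rounding to 57 first gives 57 / 0.9 = 63.3, hence 64, which is immaterial here).

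**Assumed, not in the documents.** True difference −10 and SD 19 at both visits; Week 6–Week 12 correlation r of 0.5, 0.7 or 0.8; 10% lost between Visits 3 and 4; loss depending on the Week 6 value by the rules below.

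**Formula.** Let S be the completers' mean Week 6 change minus the mean of everyone in that arm. With equal SDs at the two visits, the bias in the complete-case Week 12 difference is r × (S_Eze/Ato − S_Ato). Positive values move a −10 difference toward zero.

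**Same rule in both arms, 10% lost overall**

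| Rule | Lost, Ato / Eze/Ato | S_Ato | S_Eze/Ato | Gap | Bias at r = 0.5 / 0.7 / 0.8 | Simulated estimate |
|---|---|---|---|---|---|---|
| Odds ratio 2 per SD | 11.6% / 8.4% | −1.45 | −1.07 | 0.38 | 0.19 / 0.26 / 0.30 | −9.76 / −9.73 / −9.70 |
| Odds ratio 4 per SD | 12.7% / 7.3% | −2.73 | −1.65 | 1.07 | 0.54 / 0.75 / 0.86 | −9.45 / −9.28 / −9.12 |
| Exactly the worst 10% leave | 14.4% / 5.6% | −5.03 | −2.27 | 2.76 | 1.38 / 1.93 / 2.21 | −8.63 / −8.05 / −7.81 |

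S in the first two rows comes from numerical integration over a normal Week 6 value. In the third it is −19 × φ(z)/Φ(z), with a common cut-off at +10.2%. The simulated column used 2,000,000 patients per scenario and agrees to within simulation error (about 0.05). The third row is an extreme case.

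**Rules that differ by arm**
- The worst 10% within each arm leave: S is equal in the two arms, so the bias is 0 (simulated −9.93 to −10.02).
- Only Ato loses its worst 20%: S_Ato = −19 × 0.280/0.80 = −6.65, bias +3.3 to +5.3, estimate −6.7 to −4.7.
- Only Eze/Ato loses its worst 20%: the same size with the opposite sign, estimate −13.4 to −15.3.

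**Using Week 6.** Regress Week 12 on treatment, covariates and Week 6 in completers (treatment coefficient g, Week 6 coefficient h). Regress Week 6 on treatment and covariates in everyone (treatment coefficient a). The Week 12 contrast is g + h × a, which is what a repeated-measures likelihood gives when loss only occurs after Week 6. It returned −9.93 to −10.07 in every scenario above.

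**Scale at trial size** (63 per arm, 6,000 replicates, 10% lost). The standard error is about 3.5. Power falls from about 79% with no dependence to 78% (odds ratio 2) and 75–76% (odds ratio 4). Coverage of the 95% interval stays at 94–95%. The largest graded bias, 0.86, is 0.86 / 3.5 = 0.25 of a standard error.

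**With up-titration modelled** (assumed baseline means 95 and 125 mg/dL and 5 further points of fall after a dose increase). At 10% missing and odds ratio 2–4 per SD, the complete-case bias is about 0.2–0.8 on about −9.6, and the joint estimate stays within about 0.1. With r = 0.7 and odds ratio 4, loss in Ato only gave about −7.5 and in Eze/Ato only between −11.3 and −11.8. When loss depended only on up-titration status the bias was at most 0.07, because about 94% of Ato and 87% of Eze/Ato patients were up-titrated in that set-up, so status barely separates patients.

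**The case against.** The strongest case is that nothing of consequence turns on this. SAP 8.2 reserves inferential conclusions for the primary endpoint. Protocol 7.1 keeps patients who stop treatment in the study for lipid evaluation, an early-discontinuation visit measures lipids, and SAP 7.3 accepts a Week 12 value from Day 65 to Day 105. Lack of effect is not a listed discontinuation reason; the plan's response to a missed target is a dose increase. Under graded mechanisms the bias is a fraction of a standard error and coverage is intact. All of this stands and sets the weight of the point. It does not close the gap: withdrawal under Protocol 7.2 ends participation, and an early-discontinuation sample before Day 65 falls in the Week 6 window and is not used at Week 12.

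A reader might infer that the Week 12 difference will be understated. The documents do not support a fixed direction. That result needs the same dropout–response relation in both arms as well as a true benefit. Equal worst shares leaving each arm give no bias, and loss concentrated in Eze/Ato exaggerates the effect. For the same reason, dependence of loss on Week 6 does not by itself make the treatment difference biased.

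A reader might also infer that the dose rule itself creates the bias. It does not: loss tied only to up-titration status gives almost none. A further gradient in the LDL-C value is needed, and the documents neither show nor exclude one.

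Nor was dropping LOCF a mistake in itself. Carrying Week 6 forward would place a pre-titration value at Week 12. The criticism is that nothing replaced it and SAP 4.5 does not list it.

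**Conclusion.** The gap is in the text: the Week 12 analysis is complete-case and ignores Week 6, and no planned analysis examines loss after Visit 3. If loss depends on the Week 6 LDL-C value, the Week 12 LDL-C difference can be biased, toward zero or away from it according to how loss differs by arm.

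Under moderate assumptions with the same rule in both arms, the size is about 0.2–0.9 points on 10, against a standard error of about 3.5. Larger figures need a hard cut-off or strongly one-sided loss. The loss rate, the correlation and the mechanism are all assumptions; the documents supply none of them. The benefit of using Week 6 was shown for LDL-C only.

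This is a minor point: a cheap improvement to a secondary estimate, not a threat to the trial's conclusion.

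**What to change.** 1. **SAP 15.2.3.** For Week 12 LDL-C, take the treatment contrast from one repeated-measures model on Week 6 and Week 12 percentage change, with treatment, baseline and statin history each by visit and an unstructured covariance. At minimum, add this as a Week 12 sensitivity analysis beside the planned ANCOVA. Leave the Week 6 primary ANCOVA as it is.
2. **Reporting.** Tabulate Week 12 LDL-C missingness by arm and by Week 6 response. This shows directly whether the concern arose and in which direction.
3. **SAP 4.5.** List the removal of the protocol's LOCF rule as a change.

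Extending the model to HDL-C, non-HDL-C and total cholesterol is optional. A model for one of those lipids conditions on that lipid's own Week 6 value, not on Week 6 LDL-C, so it need not remove a dependence on LDL-C.

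Cost: SAP wording, one model call and one table, with no new data. The model relies on data being missing at random given Week 6 and on joint normality of the two visits. If the database is already locked, label the added analysis post hoc.
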